#### Outcome measures:

Primary outcome measures:

- [C]butyrate uptake
- Change in average blood glucose metabolism measured by continuous glucose meter

Exploratory outcome measures:

- [F]FDG PET glucose metabolism
- Cognition dependent mobility functions: postural sway (iSWAY), Timed Up and Go test (iTUG) measured using Mobility Lab modules (APDM, Inc., Portland, OR) 
- Dynamic balance using the Mini-BESTest 
- Spatiotemporal gait measurements using Protokinetics Zeno™ Walkway (Protokinetics LLC, Havertown, PA)
- Remainder of the clinical and laboratory test battery

Tributyrin intervention aim: BA and its prodrug tributyrin are naturally present in butter. In spite of its promise, systemic butyrate supplementation suffers from several limitations as butyrate is metabolized rapidly as soon as it enters the colonocyte via its active transport system  and resulting plasma (or brain) concentrations are very low. Tributyrin is a stable and rapidly absorbed prodrug of butyric acid offers several advantages compared to butyrate. Tributyrin is a neutral short-chain fatty acid triglyceride that is likely to overcome the pharmacokinetic drawbacks of natural butyrate as a drug . Because it is rapidly absorbed and chemically stable in plasma, tributyrin diffuses through biological membranes and is metabolized by intracellular lipases, releasing therapeutically effective butyrate over time directly into the cell. Compared with butyrate, tributyrin has more favorable pharmacokinetics  and is well tolerated . Liquid tributyrin filled into gelatin capsules and administered orally resulted in millimolar concentrations of butyrate both in plasma and inside the cell . Unlike BA, tributyrin is lipophilic with a plasma half-life of 40 minutes making it a preferred choice for systemic oral administration. Tributyrin is available over-the-counter as a supplement for patients with inflammatory bowel disease. Healus complete biotic butyrate supplement (500 mg tributyrin per

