# **Overall strategy**

#### Overview

The overarching goal of this small exploratory open-label pilot study is to explore [C]butyrate PET and [F]FDG PET glucose metabolism and clinical measures before and after open-label treatment with the SCFA prodrug tributyrin in a small pilot study in PD (n=8) and normal control older adults (n=2). Positive findings in this small exploratory pilot trial may support target engagement study of SCFA supplementation in normal adults and PD. PET and/or MRI Imaging protocols will be optional for a separate subset of 10 participants may also complete the study based on clinical or laboratory test battery alone for the exploratory hypothesis.

Timetable: This study, to be conducted over a 2-year period, will include a net total of n=20 subjects (NC, n=4; PD, n=16; total net; n=20; gross n=32 to allow for attrition). Details of the enrollment and major test procedures are listed in **table 1** below.

*Milestone* of recruitment success are net completion of 9 persons for year 1.

Table 1: Study enrollment & main       assessments	NC	PD	TOTAL
Baseline [  C]butyrate PET and [  F]FDG PET-CT & brain MRI with baseline clinical assessment	NC=2	PD=8	n=10
Post-intervention [  C]butyrate PET and [  F]FDG PET-CT & MRI	NC=2	PD=8	n=10
30-day (± 7) tributyrin intervention with pre/post clinical assessments)	NC=4	PD=16	n=20
Exploratory clinical and laboratory test battery pre and post the tributyrin supplement intervention	NC=4	PD=16	N=20
Total subject net recruitment aims 1 & 2	NC=4	PD=16	n=20*

Design: Exploratory open-label tributyrin supplementation pilot study.

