### **Statistical analysis**

We will use mixed linear modeling to assess for changes in butyrate and glucose metabolism before and after the tributyrin supplementation.

As a *post hoc* and only exploratory analyses we will regress differences in with tributyrin-induced changes of the various clinical and laboratory outcome measures.

Sample size estimation: This experiment is a first in human study of this drug for treatment of glucose changes in a neurodegenerative condition. There is a preliminary experiment of this safe drug conducted in high-fat fed mice that we base our same size justification off that showed mice receiving tributyrin showed a reduction in glucose levels compared to a comparator arm of approximately 13% with a standard deviation of 9% (PMID 22621868). If estimate a similar effect size in our cohort, estimating a mean plasma glucose of 110mg/dl at baseline, using a power of 0.8 and a two-sided alpha of 0.05 for our primary analysis that will compare pre and post tributyrin, we arrive at a total sample size of 20.

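### The sample size of 20 does not follow from its glucose inputs for a pre/post comparison, and it does not cover the butyrate PET primary, which has no designated primary region, uptake parameter or time window

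*Combined protocol and SAP*

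**What the plan says.** The Outcome measures section lists two primary outcomes with no ranking. One is carbon-11 butyrate uptake, given only as "C]butyrate uptake". The other is "Change in average blood glucose metabolism measured by continuous glucose meter".

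The Statistical analysis section plans one model for both: "We will use mixed linear modeling to assess for changes in butyrate and glucose metabolism before and after the tributyrin supplementation". It has one sample-size paragraph. The effect comes from high-fat-fed mice, which showed "a reduction in glucose levels compared to a comparator arm of approximately 13% with a standard deviation of 9"%. The paragraph adds an assumption for this cohort, "estimating a mean plasma glucose of 110mg/dl at baseline", sets the power at 0.8, and concludes: "two-sided alpha of 0.05 for our primary analysis that will compare pre and post tributyrin, we arrive at a total sample size of 20".

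The Overview in Overall strategy describes an open-label study in which everyone takes tributyrin. The net total is 20 (16 PD, 4 controls) and the gross total is 32, to allow for attrition. Table 1 plans the imaging row, "PET-CT & brain MRI with baseline clinical assessment", for 10 people (8 PD, 2 controls). For the rest, "PET and/or MRI Imaging protocols will be optional for a separate subset of 10 participants".

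On where butyrate is measured, Hypothesis 2 names brain, liver, heart and gut, Table 2 marks the PET-CT as brain/body, and the PET imaging paragraph refers to cortical and subcortical volumes of interest in general.

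**The concern.** The effect and SD come from a comparison between two arms, but the analysis compares each participant with himself or herself. A paired calculation needs the SD of the within-person change in glucose on the continuous monitor. The plan gives neither that SD nor a pre/post correlation from which to derive it, and it does not say what kind of SD the 9% is. The stated size and power therefore cannot be traced to their inputs.

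The paragraph also speaks of a single primary analysis when there are two primaries. A reader could take 20 participants at 80% power to cover butyrate uptake, which is planned in half that number and has no effect size, SD or precision stated.

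Finally, butyrate uptake is not yet one defined quantity. The plan says that positive findings may support later target engagement studies. Readers of the results will need to know which butyrate measure was the planned one. With several organs and many brain volumes available, and no uptake parameter or time window fixed, they could not tell.

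**Working it through.** **Inputs.** From Statistical analysis: difference 13%, SD 9%, baseline 110 mg/dL, power 0.8, two-sided alpha 0.05, N = 20. From Table 1: butyrate PET in 10 (8 PD, 2 controls). Standardised effect: 13/9 = 1.444. On the mg/dL scale the ratio is the same: 14.3/9.9 = 1.444.

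**Can 20 be reproduced?** Power is from the exact noncentral t. For n pairs there are n − 1 degrees of freedom and the noncentrality is d√n, where d is the mean change divided by the SD of the change.

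| Reading of the 9% | SD of change | Smallest n for 80% power | Power with 20 pairs |
|---|---|---|---|
| SD of the within-person change | 9% | 6 pairs (0.805; 5 pairs give 0.680) | above 0.999 |
| SD at each time point, correlation 0 (assumed) | 9 × √2 = 12.7% | 10 pairs (0.819; 9 pairs give 0.765) | 0.991 |
| SD at each time point, correlation 0.5 (assumed) | 9 × √(2 × 0.5) = 9% | 6 pairs | above 0.999 |

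The last two rows use SD of change = 9 × √(2(1 − r)).

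**Two parallel groups**, same inputs, noncentrality 1.444 × √(n/2) with n per group: power is 0.766 with 8, 0.820 with 9 and 0.863 with 10. The smallest design is therefore 9 per group, 18 in total. This is the closest match to 20 at the stated power and alpha. It fits the mouse source, but here there is only one treatment arm. That a two-group formula was used is a plausible explanation and cannot be confirmed.

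**Does attrition explain it?** No. The Overview calls 20 the net number and gives 32 separately as the gross number.

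**What SD would make 20 right?** At 80% power, 20 pairs detect 0.660 SD of the change. Setting 0.660 × SD = 13% gives SD = 19.7%, or 21.7 mg/dL at 110. The plan states no such figure.

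**What 20 pairs detect at 80% power** (PD and controls pooled):
- SD of change 9%: 0.660 × 9 = 5.9%, or 6.5 mg/dL at 110.
- SD of change 12.7%: 0.660 × 12.7 = 8.4%, or 9.2 mg/dL at 110.

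**Butyrate.** With no effect or SD stated, no sample size can be computed, but precision can be given in SD units. The 95% CI half-width for the mean change is t(0.975, n − 1)/√n:
- n = 10: 2.262/3.162 = 0.72 SD of the change.
- n = 8 (PD only): 2.365/2.828 = 0.84 SD.
- n = 20 (if everyone in the optional subset were also scanned): 2.093/4.472 = 0.47 SD.

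**The case against.** The study calls itself a small exploratory pilot, its only stated milestone is recruitment, and 20 is more than the stated inputs require. No participant is put at a disadvantage by the arithmetic. That stands, and it is why the point concerns clear reporting and not the size of the study.

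A reader might go further in four ways that the documents do not support.

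- **That the study is underpowered.** For glucose the stated inputs point the other way. For butyrate the plan makes no power claim that could fail.
- **That the true power for glucose is above 99%.** This holds only if the mouse SD, on one of the readings above, carries over to within-person change in people. The plan neither gives nor justifies that SD.
- **That no region is mentioned for butyrate.** Four organs are named in Hypothesis 2. The title, the volumes of interest and the grey-matter partial volume correction all point to the brain as the main interest. What is missing is a designation of one region as primary.
- **That the false-positive rate is inflated.** The plan contains no rule under which a change in any one organ, or in either primary, would count as success, so an error rate for such a rule would describe something that was not planned.

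What remains is that the plan itself separates primary from exploratory outcomes and attaches a power and an alpha to its primary analysis. Having done so, it should make the figure follow and say which primary it covers.

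**Conclusion.** The point holds as a reporting and specification gap that should be fixed. On the stated inputs a paired comparison needs 6 pairs (SD of the change 9%) or 10 pairs (9% at each time point, assumed correlation 0), not 20, so the 80% does not describe what 20 participants give. These figures treat PD and control participants as sharing one mean change and use a paired t-test as a stand-in for the mixed model, whose terms are not given.

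The calculation is silent on the butyrate primary. With the 10 planned scans, the mean change would be estimated to within about 0.72 SD of the change (0.84 SD for the 8 PD participants alone). That outcome still lacks a designated primary region, an uptake parameter and a time window.

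**What to change.** Keep N = 20.

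1. **Statistical analysis, sample size.** State that the calculation concerns continuous-monitor glucose only. Replace the 80% power statement with the paired detectable change. Suggested wording: *With PD and control participants pooled, 20 participants give 80% power to detect a mean change of 0.66 SD of the within-person change. This is 5.9% (6.5 mg/dL at 110 mg/dL) if that SD is 9%, and 8.4% if it is 12.7%. The SD is an assumption.*
2. **Same section, butyrate.** Add: *Butyrate PET is planned in 10 participants and no power is claimed. The 95% CI half-width for the mean change is about 0.72 SD of the change (0.84 SD for the 8 PD participants alone).*
3. **Outcome measures.** Before outcome data are examined, designate one butyrate region and one uptake parameter with its time window, chosen by the investigators. Label the other regions and organs exploratory.
4. **Reading the two primaries.** Say that both are reported as estimates with 95% confidence intervals and without a confirmatory claim.

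The cost is wording and one recalculation, with no extra participants or scans. The downside is that there is no formal test of the change in butyrate uptake, the first measure named in Aim 1.

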#### Background

[figure not shown]
Ketogenic diet and SCFA interventions in neurodegeneration:

The ketogenic diet based on preferential intake of predominant medium and long-chain fatty acids and minimization of carbohydrates has become a subject of recent research in metabolic and neurodegenerative disorders. Preliminary positive findings have been reported mainly from shortduration studies. Despite the benefits of this diet, health care professionals still question its safety due to the elevated serum ketones it induces and the limited dietary fiber intake . To compound the controversy, patient compliance with the program is poor due to the restrictive nature of the diet and symptoms related to energy deficit and gastrointestinal adversity during the introductory and energy substrate transition phase of the diet. Another class of fatty acids, so-called short chain fatty acid (SFCA), has been extensively studied for their role in the gut microbiome. For example SCFAs, in particular n-butyric acid (BA), acetic acid and propionic acid, are naturally present in the colon as a bacterial product of dietary fiber fermentation. Renewed interest in SCFAs has also emerged because of their ability to alter gene expression through histone deacetylase (HDAC) inhibition. HDAC has become a drug target in cancer as well as non-oncological diseases. These carboxylic acids are also of interest for their effects in the brain including memory enhancement and neuroprotection in rodent experiments. Animal and human ingestion studies of prebiotic fibers associated with brain health, such as inulin and resistant potato starch, found selective increases in the production of colonic BA and acetic acid . Similarly, intermittent fasting in MPTP-induced Parkinson's disease mice

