### Exclusion criteria:

1. *Exclusion*: (a) subjects with contra-indications to MR imaging, including pacemakers or severe claustrophobia (for participants undergoing imaging); (b) Evidence of large vessel stroke or mass lesion on MRI; (c) Regular use of anti-cholinergic, benzodiazepines or neuroleptic drugs, (d) history of significant GI disease, (e) significant metabolic or uncontrolled medical cormorbidity, (f) poorly controlled diabetes, (g) pregnancy or breast feeding, (h) dementia requiring informed assent, (i) suicidal ideation.

Recruitment: Subjects will be recruited from the University of Michigan Movement Disorder clinics, UM research studies website, and/or advertisement/flyers.

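### Use of over-the-counter tributyrin or butyrate is neither excluded nor recorded, and supplement, fibre and diet intake is not held stable, so both one-arm before/after primary comparisons could be biased.

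*Combined protocol and SAP*

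**What the plan says.** **Availability and other butyrate sources.** In the tributyrin intervention paragraph under Outcome measures, the protocol says: "Tributyrin is available over-the-counter as a supplement for patients with inflammatory bowel disease". The Background reports that ingestion studies of prebiotic fibres, namely inulin and resistant potato starch, "found selective increases in the production of colonic BA and acetic acid". It also cites a rat study in which eight weeks of inulin raised 11C-acetate PET uptake in brain, heart and liver.

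**Eligibility.** The exclusion list runs from (a) to (i). The only concomitant products it names are anti-cholinergics, benzodiazepines and neuroleptics. The nearest other items are "d) history of significant GI disease, (e) significant metabolic or uncontrolled medical cormorbidity". Neither this list nor the population description mentions supplements, butyrate, fibre or diet.

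**Recording.** Table 2 has no supplement or diet history. The daily diary described after Table 3 covers only the tributyrin dosing period, and the bottle return checks study supply.

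**Outcomes and analysis.** The primary outcomes are [11C]butyrate uptake, measured in the imaging subset of 10 (8 PD, 2 controls), and "Change in average blood glucose metabolism measured by continuous glucose meter", planned in 20. The Statistical analysis section says: "We will use mixed linear modeling to assess for changes in butyrate and glucose metabolism before and after the tributyrin supplementation". There is no untreated arm.

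**The concern.** In a one-arm study the baseline stands in for the untreated state. As the text reads, someone already taking tributyrin or butyrate can enrol, and no scheduled item would reveal it. Two errors with different mechanisms can follow:

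- **Use before or during baseline.** The participant is partly or fully treated at the first measurement, so the measured change tends toward zero.
- **A butyrate or fibre product, or a diet change, started after baseline.** The baseline is sound, but any effect on the post-treatment measurement is credited to the study capsules.

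Neither can be repaired in analysis if intake was never recorded. The pilot is meant to inform whether target engagement studies follow, and a diluted or inflated signal would mislead that decision.

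**Working it through.** **Inputs from the Statistical analysis section.** The glucose reduction is "approximately 13% with a standard deviation of 9"%, from mice compared with a comparator arm. Baseline is 110 mg/dl. The test is set by "using a power of 0.8 and a two-sided alpha of 0.05 for our primary analysis that will compare pre and post tributyrin". Stated N is 20.

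- Effect: 0.13 × 110 = 14.3 mg/dl
- SD: 0.09 × 110 = 9.9 mg/dl
- Standardised effect: 14.3 / 9.9 = 1.44

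**The plan's own figure.** A two-sample t calculation needs 9 per group, 18 in total (power 0.82). That is within two participants of 20; 10 per group gives 0.86. The paired comparison the text describes needs 6 if 9.9 is the SD of change, or 10 if 9.9 is the per-occasion SD with no within-person correlation. So 20 is reproduced only as a two-group calculation. That is a separate matter, and N is not disputed here.

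**SD of the within-person change.** SD of change = 9.9 × √(2(1 − r)). With r = 0.5 it is 9.9; with r = 0 it is 14.0. Both are shown because the plan does not say which applies.

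**Dilution.** Assume k of n participants are fully exposed at baseline and show no further change, while the rest change by 14.3 mg/dl on average.

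- Expected mean change = 14.3 × (1 − k/n)
- 2 of 20: 14.3 × 0.90 = 12.87 mg/dl (11.7% instead of 13%)
- 2 of 10: 14.3 × 0.80 = 11.44 mg/dl (10.4% instead of 13%)

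**Power.** Two-sided paired t-test at 0.05, with k fixed and normal changes (400,000 simulated trials per cell). The PET columns borrow the glucose effect size, because the documents give none for PET.

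| Share exposed (assumed) | Mean change, mg/dl | Glucose n=20, SD 9.9 | Glucose n=20, SD 14.0 | PET n=10, SD 9.9 | PET n=10, SD 14.0 |
|---|---|---|---|---|---|
| 0% | 14.30 | >0.999 | 0.99 | 0.98 | 0.82 |
| 10% | 12.87 | >0.999 | 0.97 | 0.93 | 0.70 |
| 20% | 11.44 | >0.99 | 0.91 | 0.82 | 0.57 |
| 30% | 10.01 | 0.97 | 0.80 | 0.67 | 0.44 |

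Two users of 20 is the 10% row for glucose; two of 10 is the 20% row for PET.

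**The case against.** **The named user group is largely excluded.** The supplement is said to be sold for inflammatory bowel disease, and a history of significant GI disease is an exclusion. This stands as a narrowing. It does not reach people who take butyrate products for other reasons.

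**Short half-life and fasting.** Tributyrin's plasma half-life is given as 40 minutes, and PET and sampling are done fasting in the morning. This limits acute carry-over at the baseline scan. It does not cover the longer-term effects hypothesised after about 30 days, nor the week-long glucose recording, which is not restricted to fasting.

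**No further change is a worst case, especially for fibre.** This stands. The protocol itself says butyrate is rapidly metabolised in the colonocyte, leaving very low plasma and brain levels; that is its reason for using tributyrin. Its PET evidence on fibre is from rats and uses acetate. A reader might infer that habitual fibre users would not respond and should be excluded. The documents do not show that, and steady fibre intake is present at both measurements.

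**The omission may be only apparent.** The paragraph on ineligibility and attrition has a heading but no visible text, and the content of the pre-consent screening questionnaire is not shown. The point is therefore limited to what the available text states.

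**Conclusion.** The point holds as a gap in eligibility, instructions and recording that could bias both primary outcomes. It does not show that bias will occur, because no frequency of use is given and every exposed share above is an assumption.

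For glucose, the consequence is mainly a biased estimate: 11.7% instead of 13% with 2 fully exposed users of 20, and power still about 0.97 or higher. A reader might infer that two users would take the glucose comparison well below its 80% target; the protocol's own effect size and SD do not support that. The PET subset is more fragile: two of 10 would cut power from 0.98 to 0.82 (SD of change 9.9) or from 0.82 to 0.57 (SD 14.0). Those figures rest on a borrowed effect size and on no further change in the exposed.

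It is also tempting to say that products started mid-study contaminate the baseline. They cannot; they affect the post-treatment measurement. The direction of that error is not established either, since the hypothesis says only that uptake and metabolism may change.

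**What to change.** 1. Add an exclusion for current use of tributyrin or butyrate supplements, or a washout whose length the investigators set.
2. Ask participants not to start or change such supplements, prebiotic fibre or their usual diet from the first baseline measurement (PET or glucose monitor) to the last visit. For fibre, stability and recording are enough; exclusion is not needed.
3. Record use of these products at Visits 1, 3 and 4, and plan a sensitivity analysis that leaves out exposed participants.

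The cost is one eligibility line, one instruction and one added question at three visits. A few volunteers may be excluded or delayed. The planned sample size is unchanged.

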#### Table 3: Neuropsychological characterization

able 5. Neuropsychological characterization				
Overall mental status	Montreal Cognitive Assessment Scale 			
	PD-Cognitive Rating Scale 			
Intelligence	WAIS-IV: Information 			
Attention & Cognitive	n-back test (OPTIONAL)  , Stroop Color Word			
Control	Interference Test 9			
	WAIS-IV: Digit Span (5)			
	WAIS-III: Digit Symbol-Coding 			
Language	Boston Naming Test (30 item) 			
	Controlled Oral Word Association Test (Phonemic &			
	Semantic)			
Learning & Memory	California Verbal Learning Test – II 			
Visuospatial/Construction	Clock drawing 			
	Benton Judgment of Line Orientation 			
Executive/Working	D-KEFS: Color Word Test, Verbal Fluency Test, Trail			
Memory	Making Test, Sorting Test 			
	WAIS-IV Matrix Reasoning, Digit Backwards 			
Information processing	D-KEFS: Trail Making Test 			
speed	WAIS-III: Digit Symbol-Coding 5, 23			
	Reaction time			

capsule) will be used as 1 capsule tid with meals (total of 1.5 g of tributyrin per day). If the patient cannot tolerate tributyrin we will lower the dose to one bid and if this is not tolerated than to once per day (e.g. at evening) and if this is not tolerated we will withdraw the study participant from the study. The participant will be asked to complete a daily drug diary while taking tributyrin. All supplement bottles will be returned at the end of the study for a drug accountability check.

Magnetic resonance imaging (MRI) will be performed on a 3 Tesla Philips Achieva system (Philips, Best, The Netherlands). A 3D inversion recovery-prepared turbo-field-echo was performed in the sagittal using TR/TE/TI=9.8/4.6/1041ms; turbo factor=200; single plane average; FOV=240x200x160mm; acquired Matrix = 240x200x160 slices and reconstructed to 1mm isotropic resolution. Resting-state fMRI scans will serve as a secondary outcome measure and be acquired using a 32-channel head coil and multi-band sequence , with nominal parameters: (TR/TE/FA = 720/34/52, 2mm isotropic resolution, 72 slices). Data are collected with eyes fixated on a cross for 10 minutes . Pre-processing follows our standard pipeline that includes physiologic noise reduction and thorough motion correction . Graph theory analysis will be used to identify the most highly connected nodes following published methods. Briefly, ROIs will be represented as nodes and pairwise correlations, based upon the mean time series for each ROI, will serve as weights over corresponding edges, thresholded by FDR correction, p<0.05. Change from baseline will serve as the primary measure of interest.

PET imaging will be performed in 3D imaging mode on a Biograph 6 TruePoint PET/CT scanner (Siemens Molecular Imaging, Inc., Knoxville, TN), which acquire 63 transaxial slices (slice thickness: 2.4 mm) over a 15.2 cm axial field-of-view. The i.v. injection dose for [C]butyrate PET is 18 mCi and for [F]FDG is 5 mCi. Vital signs will be obtained pre- and post-[C]butyrate injection. Images will be corrected for scatter and motion. The PET imaging frames will be spatially coregistered within subjects with a rigid-body transformation to reduce the effects of subject motion during the imaging session . Statistical parametric mapping (SPM) software (SPM12; Wellcome Trust Centre for Neuroimaging, University College, London, England [https://www.fil.ion.ucl.ac.uk/spm/software/spm12/] will be used for PET-MRI registration using the cropped T1-weighted MR volumetric scan. Freesurfer software (http://surfer.nmr.mgh.harvard.edu) will be used to define cortical and subcortical volumes-of-interest (VOI).

MRI-based PET partial volume correction: We will use the Müller-Gärtner partial volume correction technique, which is based on the assumption that white matter uptake is homogeneous and uses gray matter (GM), white matter (WM) and cerebrospinal fluid (CSF) to correct the partial volume effect in GM tissues . Using the segmented images and the assumed PET resolution, the method calculates the spill-out from WM to GM and subsequently subtracts it from the GM. Similarly, it also calculates the spill-out from the GM to the surrounding tissues and compensates for the difference to the GM. The result is a grey matter image with corrected activity values in all voxels.

